9.2.2 Serious Adverse Events

The number and percentage of subjects experiencing at least one treatment emergent serious AE (SAE) will be summarized by MedDRA primary system organ class and preferred term for each cohort.

In addition, a by-subject listing of the SAEs will be presented (the subject listing will contain all SAEs regardless of treatment emergent AE status).

9.2.3 AE with outcome of death

A by-subject listing of the deaths will be presented. All deaths occurring on-study and during follow-up will be displayed (regardless of treatment emergent AE status). The primary cause of death will also be summarized.

9.2.4 Grouped AE

Grouped AEs including Anemia, Neutropenia, Thrombocytopenia, Leukopenia, Neuropathy and Rash will be determined by medical review of the AEs, and will be summarized in the AE tables in a similar fashion as AE preferred terms.

9.3 Laboratory Parameters

For the purposes of summarization in both the tables and listings, all laboratory values will be converted to standardized units. If a lab value is reported using a non-numeric qualifier (e.g., less than (<) a certain value, or greater than (>) a certain value), the given numeric value will be used in the summary statistics, ignoring the non-numeric qualifier.

If a subject has repeated laboratory values for a given time point, the value from the last evaluation will be used.

The actual values in clinical laboratory parameters will be summarized at baseline and over time on study by treatment group; summary statistics for change from baseline of hematology, clinical chemistry, and urinalysis values will also be presented.

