5 GENERAL CONSIDERATIONS

Analysis datasets will be created according to Clinical Data Interchange Standards Consortium CDISC/Analysis Data Model (ADaM) standards. SAS v9.4 or higher software will be used to perform all data analyses (ADaM datasets, tables, figures, and listings).

Baseline will be defined as the most recent non-missing value prior to or on the same day of the first dose of glembatumumab vedotin. Generally, only pre-specified planned visits will be used in the by-visit summaries, statistical analyses and calculations of any derived safety parameters except for lab summary tables. All post baseline measurements including scheduled and unscheduled assessments will be used to derive the worst / best assessment for lab summary tables.

The primary response criterion is RECIST 1.1. Confirmation of response is required in defining best overall response (BOR) as the primary endpoint. The irRECIST is used as a secondary analysis for all efficacy endpoints except for OS.

All analyses specified in this plan will be performed by cohort. All baseline tables will include a column for each cohort and a column for overall. Unless otherwise stated, continuous variables will be summarized with n, mean, median, standard deviation, Q1, Q3, minimum and maximum, and categorical variables will be summarized with frequency counts and percentages.

Unless otherwise stated, all listings will be sorted by cohort, subject number, and then by visit date if applicable.

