9.3.1 Hematology and Clinical Chemistry

The descriptive summary table with actual lab values and change from baseline values will be generated based on protocol defined hematology parameters (i.e., Hemoglobin, Hematocrit, Mean corpuscular volume (MCV), Erythrocyte count (RBC), Leukocytes (WBC), Platelets, Neutrophils, Lymphocytes, Monocytes, and Eosinophils) and chemistry parameters (i.e., Sodium, Potassium, Chloride, Bicarbonate, Glucose (nonfasting), Blood urea nitrogen (BUN), Creatinine, Calcium, Phosphate, Alkaline phosphatase, Alanine transaminase/ Serum Glutamic Pyruvate Transaminase (ALT/SGPT), Aspartate transaminase/ Serum Glutamic Oxaloacetic Transaminase (AST/SGOT), Total protein, Albumin, Lactate Dehydrogenase (LDH), Total Bilirubin). For hematology and chemistry parameters, shift tables of the change in NCI CTCAE grade from baseline to the post-baseline by visit and worst CTCAE grade will be generated. The number and proportion of patients with directional shifts above or below the standard normal range will be summarized for selected laboratory tests.

By-subject listings of hematology and chemistry data will be presented. Laboratory values outside of normal limits will be identified in data listings and will be flagged for high and low values.

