9.5 Electrocardiograms

Electrocardiogram (ECG) assessments are planned at Screening, Day 1 of Cycle 1, and End of Treatment visit. ECG results will be summarized using shifts from baseline for the number and percentage of subjects with abnormal (clinically significant and not clinically significant, separately) and normal findings, as reported by the local investigator.

A by-subject listing for ECG data will also be presented according to eCRFs.

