16 APPENDICES

16.1 Schedule of Assessment

Visit	Screening ²	Treatment Visits ³					
		Cycle 1/ Day 1	Cycle 1/ Day 7 (Cohorts 2 and 3)	Cycle 1/ Day 14 (Cohorts 2 and 3)	Cycle 2/ Day 1	Cycle 3, 4, 5, etc./ Day 1	End of Treatment ⁴
Visit window¹	Day -28 to Day -1		+/- 1 day	+/- 1 day	+/-3 days	+/-3 days	Within 28 days post-dosing
Informed Consent, and, if applicable, HIPAA	X						
Tumor tissue ⁷	X ⁸	X ⁹					
Skin fold biopsy ⁷	X ⁸						
Medical history ¹⁰	X	X					
Physical examination ¹¹	X	X ¹²			X	X	X
Vital signs ¹³	X	X			X	X	X
ECOG performance status	X	X ¹²			X	X	X
Electrocardiogram (ECG)	X						X
Pregnancy test ¹⁴	X	X ¹²					
Hematology ¹⁵	X	X ¹²	X	X	X	X	X
Blood chemistry ¹⁵	X	X ¹²	X	X	X	X	X
Urinalysis/dipstick ¹⁵	X	X ¹²					X
Thyroid function test (Cohort 2) ¹⁵	X	X ¹²				X (Odd cycles)	X
Immunogenicity ^{16, 17}		X				X (Odd cycles)	X
PBMC collection ^{17, 18}		X			X	X (Cohorts 2 and 3, Cycle 5 only)	
PK sample collection ^{17, 19}		X			X	X (Odd cycles)	X
PD sample collection ¹⁷		X			X		X
Disease assessment ²⁰	X						
Administration of glembatumumab vedotin ²¹		X			X	X	
Administration of varlilumab ²² (Cohort 2)		X			X	X ²¹	
Administration of PD-1 targeted CPI (Cohort 3) ²³		X	X ²³				
Survival status							
Concomitant medication review ²⁴	X	X	X	X	X	X	X
Adverse event monitoring ²⁵		X	X ²⁶	X ²⁶	X	X	X

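### The ECG shift table rests on one planned post-baseline ECG and generally leaves out unscheduled on-treatment ECGs; the scope of the last-value laboratory rule should also be stated

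*SAP*

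**What the plan says.** **ECG.** SAP 5 gives the general rule for safety data: "Generally, only pre-specified planned visits will be used in the by-visit summaries, statistical analyses and calculations of any derived safety parameters". An exception follows for laboratory summary tables, and ECG is not named in it. SAP 9.5 states that ECG "assessments are planned at Screening, Day 1 of Cycle 1, and End of Treatment visit". It plans a shift from baseline across investigator categories (normal, abnormal not clinically significant, abnormal clinically significant) and a by-subject listing. It does not say which post-baseline ECG enters the shift. ECG parameters are a named safety endpoint in protocol 11.1 and SAP 2.2.2.

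**Laboratory.** SAP 9.3 states: "If a subject has repeated laboratory values for a given time point, the value from the last evaluation will be used". SAP 5 states: "All post baseline measurements including scheduled and unscheduled assessments will be used to derive the worst / best assessment for lab summary tables". SAP 9.3.1 says that "shift tables of the change in NCI CTCAE grade from baseline to the post-baseline by visit and worst CTCAE grade will be generated", and, for the listings, "Laboratory values outside of normal limits will be identified in data listings and will be flagged for high and low values".

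**The concern.** A safety table should be able to show an abnormality that arises while patients are on drug. For laboratory tests the SAP provides for this by opening the worst-value derivation to all measurements. For ECG it makes no such provision. An ECG taken during treatment because a patient had symptoms is by definition unscheduled, so under the general rule it would not normally enter the table. What enters is a reading that may come weeks after the last dose. A patient who has no End of Treatment visit contributes no planned post-baseline ECG at all.

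The laboratory issue is one of scope. A count that is low at the visit and redrawn before dosing can leave two values at one time point. Protocol Table 1 requires hematology to be reviewed before dosing and allows a window of 3 days either side for visits from Cycle 2 on. SAP 9.3 then keeps the later value, and it does not say whether that choice also feeds the grade-based tables.

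**Working it through.** The plan gives no figure to reproduce. The check sets the rules beside the schedules and counts planned ECGs.

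**Step 1. Planned ECG times.**

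| Source | Screening | Cycle 1 Day 1 | Later treatment visits | End of Treatment | Total |
|---|---|---|---|---|---|
| Protocol Table 1 (Cohorts 1-3) | yes | no | none | yes | 2 |
| SAP 16.1 | yes | no | none | yes | 2 |
| SAP 9.5 text | yes | yes | none | yes | 3 |

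Protocol Table 2 (Cohorts 4 and 5, which this SAP does not cover) also shows only Screening and End of Treatment. SAP 9.5 thus disagrees with the SAP's own appendix.

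**Step 2. Which of these are post-baseline?** SAP 5 takes as baseline the latest value on or before the day of first glembatumumab vedotin dose. A Cycle 1 Day 1 ECG is therefore a baseline value. The general instruction in protocol Table 1, to complete assessments before dosing, points the same way.

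- Under the schedules: 2 planned - 1 baseline (Screening) = 1 post-baseline.
- Under SAP 9.5: 3 planned - 2 eligible as baseline (Screening, Cycle 1 Day 1) = 1 post-baseline.

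In both cases that one is End of Treatment, which both schedules place within 28 days after the last dose. Planned ECGs after the day of first dose and before End of Treatment: 1 - 1 = 0.

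**Step 3. Can an unscheduled ECG enter the table?** The planned-visit rule in SAP 5 covers by-visit summaries, statistical analyses and derived safety parameters. Its exception is for laboratory summary tables. SAP 9.5 has no rule of its own for the worst post-baseline ECG. Followed as written, the plan generally keeps an unscheduled on-treatment ECG out of the shift table. It would appear in the by-subject listing. It would also appear as an adverse event if it met the conditions in protocol 10.2.2.1, which include symptoms, further testing or intervention, a change to treatment, or clinical significance.

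**Step 4. Laboratory rules output by output.**

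- *By-visit means and change from baseline:* one value per patient and visit is needed, so the last-value rule does a proper job.
- *By-visit grade shifts:* SAP 9.3 sets no limit on its rule, so the last value is used by default.
- *Worst-grade shifts:* SAP 5 calls for all post-baseline values. If a programmer first reduced the data to one record per time point under SAP 9.3, the result would depart from SAP 5. Nothing in 9.3 rules out that order of steps.
- *Listings:* out-of-range values are flagged.

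The documents give no rate of repeat testing and no count of unscheduled ECGs, so neither point can be turned into a number.

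**The case against.** The case for leaving the plan alone has several fair parts. The SAP 5 rule opens with a qualifier that makes it a default and not an absolute. SAP 9.5 does not call its shift table a by-visit summary, so applying the rule to it is an inference. Individual ECGs remain in the listing, SAP 9.2 counts clinically significant ECG changes in the safety evaluation, and the adverse event route exists. The sparse schedule comes from the protocol and not from an analysis rule. If few unscheduled ECGs were taken, the remedy would add few records. For laboratory data, SAP 5 expressly governs the worst assessment and can be read together with SAP 9.3 without conflict.

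Most of this stands, and it keeps the point small. It does not close the ECG gap. If the planned-visit rule applies, on-treatment ECGs stay out of the table. If it does not, the SAP has no rule for choosing among several post-baseline ECGs. A listing or an adverse event count is also no substitute for a tabulated shift on a named endpoint.

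A reader might go further and infer that the SAP throws away abnormal laboratory readings, or that both rules push toward fewer abnormalities. The documents do not support either. The worst-grade table takes in all values and the listings flag abnormal ones. A repeat may be worse than the first value, and nothing in the documents says that repeats are done mainly after abnormal results.

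**Conclusion.** The ECG point holds. As written, the only ECG summary table rests on one planned post-baseline reading, within 28 days after the last dose, with zero planned ECGs in between, and it generally leaves out unscheduled on-treatment ECGs. This assumes that the SAP 5 default is followed for the ECG table. The Cycle 1 Day 1 mismatch is a real inconsistency, but it changes neither count.

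The laboratory point is secondary. The last-value rule lacks a stated scope, affects by-visit grade shifts by default, and could be misapplied before worst grade is derived. It would be tempting to attach a percentage of missed Grade 3 or higher events to it, but any such figure would rest on repeat and recovery rates that the documents do not give.

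Neither point touches the primary response analysis, and neither is shown to change a safety conclusion. This is an inexpensive improvement to the SAP, not a flaw that threatens the trial.

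**What to change.** **SAP 9.5.** Tabulate the shift from baseline to the worst post-baseline investigator reading over all ECGs, scheduled and unscheduled. Add a footnote that unscheduled ECGs are not taken in all patients, so the table is not an incidence under uniform monitoring. Name ECG in the SAP 5 exception so that the two sections agree. Reconcile the Cycle 1 Day 1 ECG with protocol Table 1 and SAP 16.1. If such ECGs exist, state that they are baseline values.

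**SAP 9.3.** State that the last-value rule applies to by-visit means and change from baseline, and that worst CTCAE grade is derived from all post-baseline values as in SAP 5. Using the worst value at a time point in the by-visit grade shifts is optional. Whichever is chosen should be written down.

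**Cost.** A few sentences of SAP text and small programming changes, with no new assessments. The one drawback is that symptom-driven ECGs come from a selected group of patients, which the footnote discloses.

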9.3.1 Hematology and Clinical Chemistry

The descriptive summary table with actual lab values and change from baseline values will be generated based on protocol defined hematology parameters (i.e., Hemoglobin, Hematocrit, Mean corpuscular volume (MCV), Erythrocyte count (RBC), Leukocytes (WBC), Platelets, Neutrophils, Lymphocytes, Monocytes, and Eosinophils) and chemistry parameters (i.e., Sodium, Potassium, Chloride, Bicarbonate, Glucose (nonfasting), Blood urea nitrogen (BUN), Creatinine, Calcium, Phosphate, Alkaline phosphatase, Alanine transaminase/ Serum Glutamic Pyruvate Transaminase (ALT/SGPT), Aspartate transaminase/ Serum Glutamic Oxaloacetic Transaminase (AST/SGOT), Total protein, Albumin, Lactate Dehydrogenase (LDH), Total Bilirubin). For hematology and chemistry parameters, shift tables of the change in NCI CTCAE grade from baseline to the post-baseline by visit and worst CTCAE grade will be generated. The number and proportion of patients with directional shifts above or below the standard normal range will be summarized for selected laboratory tests.

By-subject listings of hematology and chemistry data will be presented. Laboratory values outside of normal limits will be identified in data listings and will be flagged for high and low values.

9.3.2 Urinalysis

A by-subject listing of Urinalysis data will be presented. The parameters to be listed include: pH, protein, glucose, blood, specific gravity, microscopic evaluations (available only if urinary infection is clinically indicated). For cohort 2, thyroid function test parameters including TSH, free T4 and T3 will be listed additionally.

9.4 Vital Signs

The actual values of vital sign parameters including temperature (Celsius), pulse rate (beats/min), respiration rate (breaths/min), systolic blood pressure (mmHg), diastolic blood pressure (mmHg), and weight (kg) will be summarized over time. Changes from baseline will also be presented. A by-subject listing for vital sign data will also be presented according to eCRFs.

9.5 Electrocardiograms

Electrocardiogram (ECG) assessments are planned at Screening, Day 1 of Cycle 1, and End of Treatment visit. ECG results will be summarized using shifts from baseline for the number and percentage of subjects with abnormal (clinically significant and not clinically significant, separately) and normal findings, as reported by the local investigator.

A by-subject listing for ECG data will also be presented according to eCRFs.

9.6 ECOG PS

Eastern Cooperative Oncology Group (ECOG) performance status will be evaluated at Screening, Day 1 of each treatment cycle, and End of Treatment visit. ECOG performance status will be summarized at baseline and each post baseline scheduled visit. Summaries will use frequency and percentage of subjects at each planned assessment time. In addition, post-baseline scores will be summarized descriptively using shifts from baseline.

A by-subject listing for ECOG data will also be presented according to eCRFs.

10 PHARMACOKINETIC, PHARMACODYNAMIC AND IMMUNOGENICITY ANALYSES

All planned analyses for PK, PD and immunogenicity will be provided in a separate report. Data listings and/or basic descriptive summaries may be presented in the Clinical Study Report.

11 INTERIM ANALYSES

No interim analysis is planned.

12 CHANGES FROM THE PLANNED ANALYSES

In the protocol, ITT population and Safety population are equivalent. For simplicity of reporting, the term of *ITT Population* is retired.

16 APPENDICES

16.1 Schedule of Assessment

Visit	Screening ²	Treatment Visits ³					
		Cycle 1/ Day 1	Cycle 1/ Day 7 (Cohorts 2 and 3)	Cycle 1/ Day 14 (Cohorts 2 and 3)	Cycle 2/ Day 1	Cycle 3, 4, 5, etc./ Day 1	End of Treatment ⁴
Visit window¹	Day -28 to Day -1		+/- 1 day	+/- 1 day	+/-3 days	+/-3 days	Within 28 days post-dosing
Informed Consent, and, if applicable, HIPAA	X						
Tumor tissue ⁷	X ⁸	X ⁹					
Skin fold biopsy ⁷	X ⁸						
Medical history ¹⁰	X	X					
Physical examination ¹¹	X	X ¹²			X	X	X
Vital signs ¹³	X	X			X	X	X
ECOG performance status	X	X ¹²			X	X	X
Electrocardiogram (ECG)	X						X
Pregnancy test ¹⁴	X	X ¹²					
Hematology ¹⁵	X	X ¹²	X	X	X	X	X
Blood chemistry ¹⁵	X	X ¹²	X	X	X	X	X
Urinalysis/dipstick ¹⁵	X	X ¹²					X
Thyroid function test (Cohort 2) ¹⁵	X	X ¹²				X (Odd cycles)	X
Immunogenicity ^{16, 17}		X				X (Odd cycles)	X
PBMC collection ^{17, 18}		X			X	X (Cohorts 2 and 3, Cycle 5 only)	
PK sample collection ^{17, 19}		X			X	X (Odd cycles)	X
PD sample collection ¹⁷		X			X		X
Disease assessment ²⁰	X						
Administration of glembatumumab vedotin ²¹		X			X	X	
Administration of varlilumab ²² (Cohort 2)		X			X	X ²¹	
Administration of PD-1 targeted CPI (Cohort 3) ²³		X	X ²³				
Survival status							
Concomitant medication review ²⁴	X	X	X	X	X	X	X
Adverse event monitoring ²⁵		X	X ²⁶	X ²⁶	X	X	X

- Imaging-based evaluation per RECIST 1.1 should be performed. Contrast-enhanced Computed Tomography (CT) of the chest, abdomen, and pelvis, as well as all other suspected disease sites is required. Magnetic Resonance Imaging (MRI) exams of the brain, abdomen, and pelvis can be performed in lieu of a CT; however, MRI exams of the chest are not recommended. In the event that a chest MRI is performed, a non-contrast chest CT is strongly recommended to evaluate the lung parenchyma. Brain and/or bone scans are required for any patients with a history of metastases to bone and/or brain or where symptomatology raises the suspicion for bone and/or brain metastases. Lesions identified on bone scans should be confirmed by a CT or MRI at baseline, and, if identified as target lesions due to soft tissue component, they should continue to be followed by the same methodology (i.e., CT or MRI scan). However, bone lesions followed as non-target disease may be subsequently followed by bone scans only. Lesions that cannot be imaged but are assessable by clinical exam may be assessed by color photography including a ruler (preferred method) or measured with calipers. Normally, all target and non-target disease sites should be evaluated at each assessment. However, for patients with non-target bone disease, bone scans need only be repeated every twelve to eighteen weeks, or more frequently if clinically indicated. The same method of assessment and the same technique should be used to characterize each identified and reported lesion at baseline and during follow-up. Target lesions selected for tumor measurements should be those where surgical resection or radiation are not indicated or anticipated.
- Unless otherwise specified, all study assessments should be performed prior to administration of study treatment(s), and may be performed up to 24 hours prior to treatment administration if assessments remain within the specified visit window.

3. In Cohort 2, varlilumab and glembatumumab vedotin will be administered as separate infusions with a break of at least 30 minutes between infusions. Varlilumab should be infused over 90 (\pm 10) minutes and administered before glembatumumab vedotin, also infused over 90 (\pm 10) minutes. Varlilumab will be administered on Day 1 of Cycles 1, 2, 4, 6, 8, and 10 only. Patients in Cohort 1 should be monitored for at least 1 hour following the last administration of study drug to monitor for infusion reaction/cytokine release syndrome/hypersensitivity reaction. Patients in Cohort 2 should be observed on Cycle 1 Day 1 for at least 2 hours after the last study drug, and for at least 1 hour at all subsequent dosing visits. Infusions should be given in a monitored setting that has ready access to an intensive care unit in case of a severe infusion reaction
4. Administration of the PD-1 targeted CPI should be continuous from the prior standard of care treatment regimen during which the most recent disease progression occurred. No more than 1 dose of a PD-1 targeted CPI should be missed between the most recent disease progression and initiation of treatment on study. Day 1 of Cycle 1 occurs with the first dose of glembatumumab vedotin which is administered on the same day as the PD-1 targeted CPI. When both glembatumumab vedotin and the PD-1 targeted CPI are administered on the same day, the drugs will be administered as separate infusions. The PD-1 targeted CPI should be the first infusion and glembatumumab vedotin administered at least 30 minutes later as the second infusion. Patients in Cohort 3 should be observed on Cycle 1 Day 1 for at least 2 hours after the last study drug, and for at least 1 hour at all subsequent dosing visits. Infusions should be given in a monitored setting that has ready access to an intensive care unit in case of a severe infusion reaction. The PD-1 targeted CPI will be administered in combination with glembatumumab vedotin until disease progression (using study screening disease assessment as baseline reference) or intolerance.
5. Additional clinic visits and monitoring (such as laboratory assessments) relevant to the administration of the PD-1 targeted CPI will be conducted in accordance with standard of care when appropriate. However, all CPI dosing and adverse events occurring between study visits will be documented in the eCRF.
6. All concomitant medication will be documented in the Case Report Form (CRF) if taken within 28 days prior to Study Day 1, and either (whichever occurs sooner): a) 28 days after last dose of study treatment or b) initiation of alternate anti-cancer therapy. In addition, all anti-cancer medications should be recorded throughout the duration of study follow-up.
7. For patients who develop grade 3 treatment-related rash and who provide appropriate consent, punch biopsies and photographs of the rash, as well as uninvolved skin, are strongly encouraged. Samples may be analyzed centrally; in these cases, collection, processing and shipping instructions will be provided separately.
8. Adverse event monitoring on Cycle 1 Day 7 and Cycle 1 Day 14 for patients in Cohorts 2 and 3 can be performed in person or by telephone to determine if the patient is experiencing any adverse events.
9. Events occurring >28 days after discontinuation of glembatumumab vedotin, >70 days after discontinuation of varlilumab (Cohort 2), or >70 days after discontinuation of the PD-1 targeted CPI (Cohort 3) are only reportable if both serious (SAE) and potentially treatment-related.
10. A delay in study treatment or performance of study visits due to holidays, weekends, inclement weather or other unforeseen circumstances will be permitted and not considered a protocol violation. However, significant delays (i.e., greater than one week) due to these reasons should be discussed with the study medical monitor to reach consensus on subsequent scheduling. See (Protocol [Section 8.5](#)) and (Protocol [Section 8.7](#)) for management of dosing delays due to toxicity.
11. Informed consent may be signed at any time prior to or during the screening period. No study-specific procedures will be performed prior to receipt of signed Informed Consent. However, assessments performed according to standard of care prior to receipt of Informed Consent may be utilized to fulfill the screening requirement, if completed within the required window for screening.
12. Patients will receive study treatment until intolerance, progression of disease, or any of the other criteria for discontinuation of study treatment (Protocol [Section 7.2.4.1.1](#)) are met. All cohorts will receive glembatumumab vedotin on a three-week cycle. Cohort 2 patients will also receive varlilumab on Day 1 of Cycles 1, 2, 4, 6, 8, and 10. Cohort 3 patients will also receive a PD-1 targeted CPI per institutional standard of care.
13. The End of Treatment Visit should be performed within 28 days after last dose of study treatment and prior to initiation of alternate therapies.
14. Disease assessments will be performed every 6 weeks (\pm 1 week) for 6 months and every 9 weeks (\pm 2 weeks) thereafter, scheduled based on the first dose of glembatumumab vedotin at CID1, until documented progression of disease or initiation of alternate anticancer therapies. For Cohorts 2 and 3, in cases of apparent progression that may reflect enhanced inflammation and/or an initial imbalance in the kinetics of tumor growth and anti-cancer immune activity, continued combination treatment may be allowed with permission granted from the Celldex Medical Monitor, until a second radiologic confirmation of progression performed at the next scheduled disease assessment (or sooner if clinically indicated) (Protocol [Section 5.5.3](#) and Protocol [Section 7.2.4.1.1](#)). If a partial or complete response is noted, a follow-up disease assessment must be done no sooner than 28 days later to confirm response. Patients who discontinue treatment in the absence of progression will continue to have tumor assessments until documented progression or initiation of alternate anti-cancer therapies. If surgical intervention or localized radiation are indicated (either for palliation or down-staging of previously non-resectable tumor), these interventions should be avoided if clinically feasible until after the 12-week response assessment. Prior to any intervention (such as surgical resection, palliative radiation or alternate anti-cancer therapy), every effort should be made to perform a tumor response assessment in order to document progression and/or confirm an objective response. Patients who undergo surgical resection or radiation in the absence of progression may continue to receive study treatment until remaining lesions meet criteria for progression of disease.

15. Subsequent to disease progression, all patients will be followed at 12 (±2) week intervals until study closure. Patients who discontinue treatment in the absence of progression will continue to have tumor assessments until documented progression or initiation of alternate anti-cancer therapies. These visits may be performed by telephone.
16. Assessment of gpNMB expression will be performed by IHC, retrospectively, at a central laboratory on FFPE Historic and Pre-entry (tumor and skin fold [axilla or groin] biopsy) samples. Skin biopsy should be 3-5 mm in diameter. Additional analyses performed centrally may also include, but are not limited to, gpNMB expression by Reverse Transcriptase Polymerase Chain Reaction (RT-PCR), examination of tumor markers using IHC or other molecular analyses, evaluation of tumor infiltrating leukocyte populations, biomarkers related to immune activation and localization of glembatumumab vedotin, CR011, or MMAE at the tumor site in post-treatment samples. Sample collection, processing and shipping instructions will be provided separately.
17. Historic FFPE samples must represent the advanced stage of disease (Stage III or IV). Pre-entry FFPE samples must be obtained within 12 weeks prior to study entry, be subsequent to the last systemic anticancer therapy received, and be post-tumor progression. For patients who must undergo biopsy to obtain a FFPE Pre-entry sample, biopsy sites must be soft tissue tumor or visceral lesions that can be biopsied with acceptable clinical risk (as judged by the investigator). The biopsy site chosen should not have been previously irradiated and must be distinct from RECIST 1.1 target lesions. Tissue from multiple previous collection dates should also be submitted, when available/feasible, in order to further understand how gpNMB levels may change over time and/or with cancer stage. Skin biopsies (Cohort 2) must be obtained within 12 weeks of study entry.
18. At recurrence, biopsy and central analysis of recurrent tumor is optional but strongly encouraged. Similarly, in the event of tumor resection or biopsy performed per standard of care anytime during treatment or following tumor progression, submission of these tissue samples for central analysis is strongly encouraged.
19. Medical history includes demography, melanoma history, previous surgeries/therapy, and pre-existing diseases. At Cycle 1, Day 1, medical history is updated prior to administration of study drug.
20. Complete physical exam should be performed at screening; thereafter, symptom-directed exams are acceptable.
21. Assessments do not need to be repeated if completed within the previous 24 hours as part of the screening assessment.
22. Vital signs to include height (at screening only), weight, respiration, pulse, temperature, and resting systolic and diastolic blood pressure. In Cohort 2 on glembatumumab vedotin and varlilumab dosing days, vital signs should be assessed pre-infusion, at 45 (±15) minutes during each infusion, and within one- half hour following completion of each infusion. In Cohort 3, vital signs should be assessed for each glembatumumab vedotin infusion as follows: pre-infusion, at 45 (±15) minutes during the infusion, and within one-half hour following completion of the glembatumumab vedotin infusion. Additionally, when the PD- 1 targeted CPI is administered with or without glembatumumab vedotin dosing, vital signs should be assessed prior to each PD-1 targeted CPI infusion and additionally, as necessary, per clinical and institutional standards. (Note: weight is only assessed once per visit.)
23. Serum or urine pregnancy test only for women of childbearing potential. Patients of non-childbearing potential include those who are ≥60 years, surgically sterilized, or postmenopausal with absence of menses for at least 1 year. However, women <60 with therapy-induced amenorrhea will require a pregnancy test unless additional evidence (oophorectomy or serial measurement of FSH and/or estradiol) are available to ensure postmenopausal status.
24. Laboratory assessments must include the following, when indicated. Hematology results must be reviewed prior to dosing. For patients in Cohort 2, liver function tests (i.e., ALT, AST, and total bilirubin) and creatinine must also be reviewed prior to dosing. In addition, in Cohort 2, thyroid function tests must be performed at screening, at Cycle 1, at every odd cycle (i.e., Cycles 3, 5, 7, etc.), and at End of Treatment.

	Clinical Chemistry:	Urinalysis
n	Sodium	pH
muscular volume (MCV)	Potassium	Protein
count (RBC)	Chloride	Glucose
(WBC)	Bicarbonate	Specific gravity
	Glucose (nonfasting)	Blood
	Blood urea nitrogen (BUN)	
	Creatinine Calcium	Microscopic examination must be performed at baseline and, if clinically indicated, at subsequent visits (if urinary infection is suspected then a negative urine culture is required prior to enrollment.)
	Phosphate	
	Alkaline phosphatase	
	Alanine transaminase (ALT/SGPT) Aspartate transaminase (AST/SGOT) Total protein	
	Albumin	Thyroid Function Test (Cohort 2 only)
l should be reported consistently the study as either an absolute erred) or as a percentage.	Lactate Dehydrogenase (LDH)	TSH
	Total Bilirubin	Free T4 and T3
		Free T4 and free T3 performed at screening, and then only if TSH is abnormal at subsequent visits.

25. Samples for immunogenicity will be collected prior to dosing on Day 1 of “odd” cycles (i.e., Cycles 1, 3, 5, 7, etc.).
26. Analyses will be performed centrally. Sample collection, processing and shipping instructions will be provided separately.
27. For Peripheral Blood Mononuclear Cell (PBMC) collection on Cycle 1/Day 1 and Cycle 2/Day 1, samples are collected prior to dosing. For Cohort 1 an additional sample is collected at End of Treatment. For Cohort 2s and 3 an additional

sample is collected on Cycle 5/Day 1 prior to dosing. Analyses may include (but are not limited to) examination of gpNMB expression (and/or potential binding partners for gpNMB) on myeloid suppressor cells; peripheral leukocytes; circulating tumor cells; and other immune response cells of interest. Additional analysis may include response assessment to potentially relevant tumor antigens and analysis of myeloid derived suppressor cells. Details on sample collection and handling will be provided separately. PBMC samples will be collected until such time Celldex informs the sites that further data is not needed.

28. Cohort 1: On Day 1 of Cycle 1 and 2 only, glembatumumab vedotin PK samples will be collected prior to dosing and at end of infusion (at or within 30 minutes after completion of infusion). A PK sample will also be collected at the End of Treatment visits.
29. Cohort 2: On Day 1 of Cycles 1, 2, and 5, a total of three PK samples will be collected on each day for glembatumumab vedotin and varlilumab PK analysis. PK samples will be collected prior to dosing of varlilumab, at end of varlilumab infusion (at or within 10 minutes after completion of infusion), and at end of glembatumumab vedotin infusion (at or within 10 minutes after completion of infusion). On Day 1 of Cycles 3, 7, and subsequent odd cycles, only one PK sample will be collected prior to the first infusion. An additional sample should be drawn as soon as possible for any patients who experience an infusion reaction. A PK sample will also be collected at the End of Treatment visits.
30. Cohort 3: On Day 1 of Cycles 1, 2, and 5, a total of two PK samples will be collected on each day for glembatumumab vedotin PK analysis. PK samples will be collected prior to dosing of glembatumumab vedotin and at end of infusion (at or within 10 minutes after completion of infusion). On Day 1 of Cycles 3, 7, and subsequent odd cycles, only one PK sample will be collected prior to the first infusion. An additional sample should be drawn as soon as possible for any patients who experience an infusion reaction. A PK sample will also be collected at the End of Treatment visits.
31. For Cohorts 1, 2, and 3, analysis may also include circulating soluble gpNMB levels or other soluble molecules.
